### **9.8 Interim analysis**

When the 64th subject has reached the primary endpoint (or been censored because of loss to follow-up), a futility analysis will be performed.

The futility analysis will use a stochastic curtailment approach (Crowley and Anhkerst, Clinical Trials in Oncology, 2nd ed p 233), as computed in PASS 14.0.6. If at the interim analysis, the conditional power (i.e. the probability that the study will go on to reject the null hypothesis, given the observed data at the interim analysis) is below 20%, the study will stop. This futility analysis will be carried out by the statisticians at the MCC Biostatistics Shared Resource, using a one-sided logrank test at the 5% significance level.

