#### **10.4 Data and Safety Monitoring/Auditing**

Data and Safety reporting will be supported by the study statisticians according to the attached monitoring plan (Appendix C and D). A series of comprehensive safety and data monitoring reports will be generated every six months for review by the study team in addition to the annual DSMB report described below.

In addition to adverse event monitoring and clinical oversight by the principal investigator and co-investigators, quality assurance of the study will be performed by the clinical trials office internal monitor. Monitoring intervals will be dependent upon the number of patients enrolled and the complexity of the study.

This study will also use the UCSD Moores Cancer Center Data Safety and Monitoring Board (DSMB) to provide oversight in the event that this treatment approach leads to unforeseen toxicities. Data from this study will be reported annually and will include:

- 1) the protocol title, IRB protocol number, and the activation date of the study.
- 2) the number of patients enrolled to date
- 3) the date of first and most recent patient enrollment
- 4) a summary of all adverse events regardless of grade and attribution
- 5) a response evaluation for evaluable patients when available
- 6) a summary of any recent literature that may affect the ethics of the study.

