### Stopping/Halting Rules

At accrual of 64 patients, a futility analysis will be performed. The stopping rule is stated in section protocol synopsis.

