## 2. Protocol Synopsis

Planned Accrual: N= 128; approximately 60-70 CRS/HIPEC procedures are performed annually at UCSD.

Study Design: The proposed study is a prospective, randomized controlled phase 2 trial. Subjects will be assigned to either placebo or alvimopan groups according to a block randomization.

Primary Objective: To determine the efficacy of alvimopan to reduce postoperative ileus in patients undergoing CRS/HIPEC, as measured by the composite of time to recovery of upper and lower GI function.

Treatment Description: Alvimopan (12 mg) or Placebo 30 minutes – 5 hours prior to surgery, then twice daily (BID) starting POD 1 for a maximum of 7 days or until hospital discharge.

Primary Endpoint(s): Time to either 1st solid food or 1st bowel movement postoperatively, whichever is later.

Study Stopping Rules:

At accrual of 64 patients, a futility analysis will be performed. If the conditional power (as computed for log-rank tests) is less than 10% at this halfway point, we will suspend the study. The conditional power threshold of 10% was chosen based on boundaries set in Jennison and Turnbull, as well as with consideration to the probability of stopping early based on a series of effect sizes. If the null hypothesis is true (i.e. a hazard ratio of 1), the study will stop early at the interim to fail to reject the null hypothesis 69.49% of the time. Under the alternative hypothesis, the study will stop early 10.35% of the time while maintaining a type II error rate of 20%.

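### The single futility look has two conditional-power thresholds, 20% in Section 9.8 and 10% in Appendix C, and the only stop rates given do not describe the 20% rule

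*Combined protocol and SAP*

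**What the plan says.** Section 9.8 plans one futility analysis, once the 64th "subject has reached the primary endpoint (or been censored because of loss to follow-up), a futility analysis will be performed". It uses stochastic curtailment with a one-sided log-rank test at 5%, and cites a textbook page and a software version. Conditional power is described as "the probability that the study will go on to reject the null hypothesis, given the observed data at the interim analysis", and if it "is below 20%, the study will stop".

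Appendix C places the look at accrual of 64 patients. Its Executive Summary gives no threshold but adds: "The stopping rule is stated in section protocol synopsis". That synopsis says that if conditional power "is less than 10% at this halfway point, we will suspend the study". It defends 10% by citing published boundaries and says the choice was made "with consideration to the probability of stopping early based on a series of effect sizes". It also gives operating characteristics. With no treatment effect (HR 1) it states that "the study will stop early at the interim to fail to reject the null hypothesis 69.49% of the time"; the corresponding early-stop rate for the alternative is 10.35%, with a type II error of 20%.

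Three other places bear on the point:
- Section 10.4 attaches Appendices C and D as the monitoring plan.
- Appendix D, part III, says the report synopsis is drawn from the research plan. Part IV says stopping-rule tables go into the interim futility report.
- Section 9.2 notes that its 80% power is not adjusted for the look.

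**The concern.** This is the only stopping rule the documents state, and it has two cut-offs. Appendix C gives reasons for its 10%, so the figure does not look like a typing slip. No order of precedence is stated, so whoever runs the look would have to choose a threshold, possibly with the interim result in hand. That defeats the purpose of prespecifying it.

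Two further gaps widen the problem. Conditional power depends on the effect assumed for the patients still to come (the observed trend, the design HR or no effect), and neither text writes that assumption out. The only stop probabilities in the documents are attached to the 10% rule. If they do not carry over to a 20% rule, a reader of Section 9.8 cannot tell how often the trial would be stopped when the drug works.

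**Working it through.** **Inputs.** HR 1.59, one-sided 5%, 1:1 allocation, 122 patients in the calculation and 128 enrolled (Sections 9.1 and 9.2); look at 64 patients (Section 9.8, Appendix C). Assumptions: nearly every patient has an event, the final critical value is 1.645, and Appendix C's alternative is HR 1.59. Ranges run between the Schoenfeld and Freedman approximations.

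**Fixed design.** The expected final Z (drift) θ with D events is √D·ln(1.59)/2 (Schoenfeld) or √D·(0.59/2.59) (Freedman). With D = 122, θ is 2.561 or 2.516, and power Φ(θ − 1.645) is 82.0% or 80.8%. This agrees with the 82% in the Study Summary and roughly with the 80% in Section 9.2.

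**Bounds.** At information fraction t with interim statistic Z1:
- current trend: CP = Φ((Z1/√t − 1.645)/√(1−t))
- design HR: CP = Φ((Z1·√t + θ(1−t) − 1.645)/√(1−t))

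Solving for Z1 gives the stopping bound b. The stop probability is Φ(b) under HR 1 and Φ(b − θ√t) under HR 1.59. Power with the look is P(Z1 ≥ b, Z2 ≥ 1.645), bivariate normal with correlation √t.

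Example at t = 0.5, current trend:
- 10%: b = (1.645 − 1.282 × 0.707) × 0.707 = 0.522
- 20%: b = (1.645 − 0.842 × 0.707) × 0.707 = 0.742

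**Results at 61 of 122 events**

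| Rule | Stops, HR 1 | Stops, HR 1.59 | Power with the look |
|---|---|---|---|
| Appendix C as stated (10%) | 69.49% | 10.35% | 80% (type II error 20%) |
| 10%, current trend | 69.9% | 9.9–10.4% | 77.4–78.7% |
| 20%, current trend | 77.1% | 14.3–15.0% | 75.0–76.3% |
| 10%, design HR | 22–23% | 0.5–0.6% | 80.8–82.0% |
| 20%, design HR | 37–38% | 1.6–1.9% | 80.6–81.8% |

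Appendix C's two stop rates are reproduced by the 10% current-trend rule at about half information, and not by a 20% rule on either assumption. Moving the look to 64 of 122 events (t = 0.525) leaves the pattern unchanged: 70.9% and 9.6–10.2% for 10% current trend, 78.0% and 13.9–14.7% for 20% current trend, 42–43% and 1.9–2.3% for 20% at the design HR.

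**Where the two texts disagree, if both use the current trend.** The interim HR at the bound is exp(2b/√d), with d interim events:

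| Look | HR at 10% bound | HR at 20% bound | Opposite decisions, HR 1 | Opposite decisions, HR 1.59 |
|---|---|---|---|---|
| 61 of 122 | 1.143 | 1.209 | 7.2% | 4.4–4.6% |
| 64 of 122 | 1.148 | 1.213 | 7.0% | 4.3–4.5% |
| 64 of 128 | 1.139 | 1.204 | 7.2% | 4.2–4.3% |

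**Simulation check.** A log-rank simulation (20,000 runs per cell, exponential times, no censoring, blocks of 4) at 61 of 122 gave 69.3%, 10.6% and power 77.5% for 10% current trend, and 76.6%, 15.1% and 75.0% for 20% current trend.

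**Type II error.** For 10% current trend it is 21.3–22.6% at 61 of 122, 21.0–22.3% at 64 of 122 and 19.6–20.9% at 64 of 128. Appendix C's 20% is thus not contradicted, but it is unexplained and probably slightly optimistic.

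**The case against.** The strongest reply is that Section 9.8 plainly governs. Section 10.4 says reporting, not decision-making, follows the attached plan. Appendix C is largely a fill-in report template, and Appendix D says its synopsis is taken from the research plan, which makes it derivative. This has some force, but no document states which text prevails. Appendix C calls its synopsis text the stopping rule and argues for 10% on its own grounds. If it is meant to be derived from the protocol, the two should agree.

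Second, Section 9.8 cites a textbook and a software version, which may fix the assumed effect. They could not be checked, so the supportable claim is only that the protocol does not write the effect out.

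Third, the current-trend reading of Appendix C is an inference, since Appendix C names neither the trend assumption nor the alternative HR. A 20% rule would reach 69.49% only with an intermediate remaining effect of about HR 1.28, which nothing in the documents suggests.

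Fourth, the practical weight is moderate. The zone of opposite decisions is narrow, a futility-only stop does not inflate type I error, and Section 9.2 already discloses that power is unadjusted. The figures also assume almost no censoring, whereas Section 2.3 censors patients discharged before recovery. With fewer events, an effective arm would be stopped more often. The type II figure and the trigger wording (64th outcome against accrual of 64, about 1–2 patients apart) are minor. None of this removes the conflict between the thresholds.

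**Conclusion.** The concern holds and must be fixed. The contradiction between 20% and 10% is plain from the text and needs no calculation. Its size, given HR 1.59, near-complete events and the current trend in both rules, is an interim HR band of about 1.14 to 1.21 with opposite decisions, reached in 7.0–7.2% of trials under HR 1 and 4.2–4.6% under HR 1.59.

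The unstated assumption matters more than the threshold: at 61 of 122 events a 20% rule stops 77.1% of null trials on the current trend but only 37–38% at the design HR. Appendix C's published rates best fit a 10% current-trend rule. The fit does not identify the exact event count. The risk that Section 9.8 stops a trial of an effective drug is not documented.

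**What to change.** State one threshold, one assumed effect for the remaining data and one trigger, chosen by the sponsor, in identical terms in Section 9.8 and in Appendix C (Stopping/Halting Rules, Protocol Synopsis and section 11). Use one word for the action, since Section 9.8 says stop and Appendix C says suspend.

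For the rule kept, give the stop probabilities under HR 1 and HR 1.59 and the power including the look, and replace Appendix C's type II error with the matching value. At 122 events that power is about 77–79% for 10% current trend, 75–77% for 20% current trend, and 81–82% for either threshold at the design HR. The 82% in the Study Summary may stay as a fixed-design figure if it carries Section 9.2's note that power is not adjusted for the look.

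The cost is wording in two places, a short note in the summary and one recalculation. Stated power falls by about 3 points (10% current trend) to 6 points (20% current trend) from the fixed-design 80.8–82.0%, and hardly at all at the design HR. No extra patients are needed.

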## **9.9 Safety Analysis**

Safety will be assessed by summarizing and analyzing AEs during the intervention period. Adverse events will be coded according to established Medical Dictionary for Regulatory Activities (MedDRA) terms and summarized by MedDRA System Organ Class and Preferred Term. Treatment-emergent adverse events (TEAE) will be defined as events that first occurred or worsened on or after randomization.

An overview of AEs, including the number and percentage of participants who died, suffered SAEs, discontinued due to AEs, and who suffered TEAEs, will be provided. A comparison between intervention arms will be performed. Summaries of AEs within system organ class will be provided for: (1) pre-existing conditions, (2) TEAEs, and (3) SAEs. Discontinuations due to AEs will also be listed.

## **10.0 STUDY MANAGEMENT**

---

### **10.1 Conflict of Interest**

Any investigator who has a conflict of interest with this study (patent ownership, royalties, or financial gain greater than the minimum allowable by their institution, etc.) must have the conflict reviewed according to UCSD conflict of interest policy.

### **10.2 Institutional Review Board (IRB) Approval and Consent**

The IRB should approve the consent form and protocol prior to any study-related activities. It is expected that the IRB will have the proper representation and function in accordance with federally mandated regulations.

In obtaining and documenting informed consent, the investigator should comply with the applicable regulatory requirement(s), and should adhere to Good Clinical Practice (GCP) and to ethical principles that have their origin in the Declaration of Helsinki.

Before recruitment and enrollment onto this study, the patient will be given a full explanation of the study and will be given the opportunity to review the consent form. Each consent form must include all the relevant elements currently required by the FDA Regulations and local or state regulations. Once this essential information has been provided to the patient and the investigator is assured that the patient understands the implications of participating in the study, the patient will be asked to give consent to participate in the study by signing an IRB-approved consent form.

Prior to a patient's participation in the trial, the written informed consent form should be signed and personally dated by the patient and by the person who conducted the informed consent discussion.

### **10.3 Subject Data Protection**

In accordance with the Health Information Portability and Accountability Act (HIPAA), subjects who have provided written informed consent must also sign a subject authorization to release medical information to the study Sponsor and allow a regulatory

authority, or Institutional Review Board access to subject's medical information relevant to the study.

#### **10.4 Data and Safety Monitoring/Auditing**

Data and Safety reporting will be supported by the study statisticians according to the attached monitoring plan (Appendix C and D). A series of comprehensive safety and data monitoring reports will be generated every six months for review by the study team in addition to the annual DSMB report described below.

In addition to adverse event monitoring and clinical oversight by the principal investigator and co-investigators, quality assurance of the study will be performed by the clinical trials office internal monitor. Monitoring intervals will be dependent upon the number of patients enrolled and the complexity of the study.

This study will also use the UCSD Moores Cancer Center Data Safety and Monitoring Board (DSMB) to provide oversight in the event that this treatment approach leads to unforeseen toxicities. Data from this study will be reported annually and will include:

- 1) the protocol title, IRB protocol number, and the activation date of the study.
- 2) the number of patients enrolled to date
- 3) the date of first and most recent patient enrollment
- 4) a summary of all adverse events regardless of grade and attribution
- 5) a response evaluation for evaluable patients when available
- 6) a summary of any recent literature that may affect the ethics of the study.

#### **10.5 Adherence to the Protocol**

Except for an emergency situation in which proper care for the protection, safety, and well-being of the study patient requires alternative treatment, the study shall be conducted exactly as described in the approved protocol.

##### **10.5.1 Emergency Modifications**

Investigators may implement a deviation from, or a change of, the protocol to eliminate an immediate hazard(s) to trial subjects without prior IRB approval.

For any such emergency modification implemented, a IRB modification form must be completed within five (5) business days of making the change.

##### **10.5.2 Other Protocol Deviations/Violations**

All other planned deviations from the protocol must have prior approval by the Principal Investigator and the IRB. According to the IRB, a protocol deviation is any unplanned variance from an IRB approved protocol that:

- Is generally noted or recognized after it occurs
- Has no substantive effect on the risks to research participants
- Has no substantive effect on the scientific integrity of the research plan or the value of the data collected
- Did not result from willful or knowing misconduct on the part of the investigator(s).

An unplanned protocol variance is considered a violation if the variance:

- Has harmed or increased the risk of harm to one or more research participants.

- Has damaged the scientific integrity of the data collected for the study.
- Results from willful or knowing misconduct on the part of the investigator(s).
- Demonstrates serious or continuing noncompliance with federal regulations, State laws, or University policies.

**Protocol Deviations:** Personnel will report to any sponsor or data and safety monitoring committee in accordance with their policies. Deviations should be summarized and reported to the IRB at the time of continuing review.

**Protocol Violations:** Study personnel should report violations within one (1) week of the investigator becoming aware of the event using the same IRB online mechanism used to report Unanticipated Problems.

### **10.6 Amendments to the Protocol**

Should amendments to the protocol be required, the amendments will be originated and documented by the Principal Investigator. It should also be noted that when an amendment to the protocol substantially alters the study design or the potential risk to the patient, a revised consent form might be required.

The written amendment, and if required the amended consent form, must be sent to the IRB for approval prior to implementation.

### **10.7 Record Retention**

Study documentation includes all Case Report Forms, data correction forms or queries, source documents, Sponsor-Investigator correspondence, monitoring logs/letters, and regulatory documents (e.g., protocol and amendments, IRB correspondence and approval, signed patient consent forms).

Source documents include all recordings of observations or notations of clinical activities and all reports and records necessary for the evaluation and reconstruction of the clinical research study.

Government agency regulations and directives require that the study investigator must retain all study documentation pertaining to the conduct of a clinical trial. In the case of a study with a drug seeking regulatory approval and marketing, these documents shall be retained for at least two years after the last approval of marketing application in an International Conference on Harmonization (ICH) region. In all other cases, study documents should be kept on file until three years after the completion and final study report of this investigational study.

### **10.8 Obligations of Investigators**

The Principal Investigator is responsible for the conduct of the clinical trial at the site in accordance with Title 21 of the Code of Federal Regulations and/or the Declaration of Helsinki. The Principal Investigator is responsible for personally overseeing the treatment of all study patients. The Principal Investigator must assure that all study site personnel, including sub-investigators and other study staff members, adhere to the study protocol and all FDA/GCP/NCI regulations and guidelines regarding clinical trials both during and after study completion.

The Principal Investigator at each institution or site will be responsible for assuring that all

the required data will be collected and entered onto the Case Report Forms. Periodically, monitoring visits will be conducted and the Principal Investigator will provide access to his/her original records to permit verification of proper entry of data. At the completion of the study, all case report forms will be reviewed by the Principal Investigator and will require his/her final signature to verify the accuracy of the data.

## 12.0 APPENDICES

---

### Appendix A. ECOG Performance Status

ECOG Performance Status Scale	
Grade	Descriptions
0	Normal activity. Fully active, able to carry on all pre-disease performance without restriction.
1	Symptoms, but ambulatory. Restricted in physically strenuous activity, but ambulatory and able to carry out work of a light or sedentary nature (e.g., light housework, office work).
2	In bed < 50% of the time. Ambulatory and capable of all self-care, but unable to carry out any work activities. Up and about more than 50% of waking hours.
3	In bed > 50% of the time. Capable of only limited self-care, confined to bed or chair more than 50% of waking hours
4	100% bedridden. Completely disabled. Cannot carry on any self-care. Totally confined to bed or chair
5	Dead.

## Appendix B. Postoperative Bowel Function Diary

### DIARY INSTRUCTIONS:

- Note the date and time of day you had each event.
- In the comment section, please include any any uncertainties regarding date or time.
- If you have any questions, please contact your nurse to contact the study staff listed in your informed consent form.

EVENT	DATE (MO-DD-YYYY)	TIME OF DAY	COMMENTS
Example.	03-15-2017	9:00 AM	
First Postoperative Flatus			
First Postoperative Bowel Movement			
First Solid Food (without significant nausea or vomiting within 4 hours)			

## 1. Executive Summary

### Report Overview

This report reviews enrollment and safety data available in the study VELOS database as of xxxx. Summary tables are provided in sections 6-15. Additional tables and figures referenced in the report are provided in the Appendices.

### Study Site Status

This is a single site trial at UCSD. It was activated 02/28/2018.

### Enrollment Status

XXX subjects have been screened for this study.

XXX subjects have been enrolled.

### Early Discontinuation/Off Treatment Status

XXX treated subjects have been discontinued (withdrawn) from the study. XXX treated subjects have completed treatment. Details are specified in section Early Discontinuation/Off Treatment.

### Stopping/Halting Rules

At accrual of 64 patients, a futility analysis will be performed. The stopping rule is stated in section protocol synopsis.

### Safety Summary

XXXX adverse events have occurred in XXX subjects. XXX serious adverse events have occurred in XXX subjects.

Of the XX adverse events: XX were mild (grade 1), XX were moderate (grade 2) and XX were severe (Grade 3+).

